### **8.2.1. Inclusion Criteria**

Patients must meet all the inclusion criteria below to be eligible for inclusion in the study:

1. *Evidence of a personally signed and dated informed consent form indicating that the patient (or his/her legal representative) has been informed of all aspects relevant to the study. Informed consent will only be obtained from patients who are still alive.*
2. *Aged 18 or over.*
3. *Histologically confirmed diagnosis of advanced kidney cancer, with at least one radiological evaluation of the disease in accordance with RECIST 1.1 criteria*

4. *Treatment with axitinib as second-line or later with a PFS equal to or greater than 9 months, or with disease progression in the first response assessment*

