**Analysis population****All analyses will be performed with evaluable patients.**

The CRF contains the information related to the eligibility criteria as binary variable (Yes/No) for each of the described items.

Several of these criteria can be verified with the data recorded in the CRF. This verification is performed in order to prevent the inclusion of non-evaluable participants in the statistical report and prior to the start of any analysis.

These patients will be considered screening failure, and in the statistical report they will thus be included in a table of patient disposition together with the patients screening failure initially confirmed by the sponsor.

The criteria to be verified in the patient CRFs to define the evaluable population are described below:

- An "evaluable" patient must have received at least one dose of axitinib prior to inclusion in the study: it must be verified that the "Starting dose" and the "Treatment start date with axitinib" have been specified in "Treatment with axitinib". This date must be prior to the date of signing the informed consent (for patients who are still alive at enrolment).

- Inclusion requirement *Patients must have received axitinib as second-line treatment or further line*: it must be verified that there is information concerning a first-line treatment in the "First-line treatment" section.

- IC1: *Evidence of a personally signed and dated informed consent document indicating that the patient (or his/her legal representative) has been informed of all relevant aspects of the study. Informed consent will only be obtained from patients who are still alive.*

It must be verified that the date of signing the informed consent is specified (for patients who are still alive at enrolment).

Noted that for patients already dead before the study inclusion, the CII could be "No".

- IC2: *Aged 18 or over.*

It must be verified that the age calculated with respect to the date of the baseline visit is  $\geq 18$  years.

- IC3: *Histologically confirmed diagnosis of advanced renal cell carcinoma, with at least one radiological evaluation of the disease according to RECIST 1.1 criteria.*

It must be verified that the following data have been indicated: Date of first diagnosis, Tumour stage at disease diagnosis, Date of advanced disease diagnosis, Stage of advanced disease, Metastasis location, Best treatment response (first-line treatment).

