- IC4: *Treatment with axitinib, as second-line or further line treatment and with progression-free survival PFS of 9 months or more or with disease progression at the first response assessment.*

It must be verified that in "Treatment with axitinib", "Treatment line in which it has been received" is  $\geq 2$ .

It must be verified that the patient meets one of the following two conditions:

- "*Progression-free survival PFS of 9 months or more*": the time from the start of treatment with axitinib to disease progression or death by any cause is  $\geq 9$  months (see definition of PFS in section 7. Definition of variables).

or

- "*Disease progression at the first response assessment*": PD has been indicated in "Treatment with axitinib/ Best response to treatment".

If there is a contradiction between the binary variables and the information shown in the CRF, the latter shall be assumed valid.

A list of candidate patients who are non-evaluable must be made, and after approval or rectification by the study sponsor/coordinator, the list of non-evaluable patients who will be excluded from the analyses will be closed.

The sponsor will be informed of the number of non-evaluable study patients for the analysis and the reasons for non-inclusion, for consultation and confirmation prior to starting the analyses.

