### **5 ANALYSIS GROUPS/POPULATIONS**

#### **5.1 FULL ANALYSIS SET**

The full analysis set [FAS] includes all evaluable patients, i.e. all patients who meet all the inclusion criteria and none of the exclusion criteria and have received at least one dose of axitinib prior to inclusion in the study.

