#### **5.2 SUBGROUPS**

For some of the study objectives, the following two groups of patients with extreme responses to the drug are defined (see definition in point 7. Definition of variables):

- “Long-term responders to axitinib”: Patients who have a PFS of at least 9 months with the drug.
- “Patients primary refractory to axitinib”: Patients with disease progression at the first assessment after the initiation of treatment (estimated PFS  $\leq 3$  months). It means, patients with best response to axitinib=PD.

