 $(\text{Dose increase date or Dose reduction date} - \text{Start date of treatment with axitinib}) / 30.4375$
  - Duration (months) of subsequent treatments =  
 $(\text{Date of end of subsequent treatment or of latest follow-up if not suspended} - \text{Date of start of subsequent treatment}) / 30.4375$ . In the case of several subsequent treatments per patient, proceed as follows: the duration in months of each of the subsequent treatments will be calculated (from the start date to the end date or last check if it continues). This will be done for all subsequent treatments and then proceed to make the sum per patient of all durations of subsequent treatments

- Progression-Free Survival (PFS, in months) =  
 (Date of Disease Progression on treatment with axitinib or death from any cause – Date of start of treatment with axitinib) / 30.4375  
 If there is no progression or death, the case is censored as  
 PFS (months) = (Date of latest follow-up – Date of start of treatment with axitinib) / 30.4375
- Time to progression (TTP, in months) =  
 (Date of Disease Progression – Date of start of treatment with axitinib) / 30.4375  
 If there is no progression, the case is censored as  
 TTP (months) = (Date of latest follow-up – Date of start of treatment with axitinib) / 30.4375
- Overall Survival (OS, in months) = (Date of death – Date of start of treatment with axitinib) / 30.4375  
 If death has not occurred, the case is censored as  
 Overall Survival (OS, in months) = (Date of latest follow-up – Date of start of treatment with axitinib) / 30.4375
- Overall Survival since the start of first-line treatment (OS, in months) = (Date of death – Date of start of first-line treatment) / 30.4375  
 If death has not occurred, the case is censored as  
 Overall Survival (OS, in months) = (Date of latest follow-up – Start date of first treatment) / 30.4375
- Patient subgroups
  - A-Long-term responders: comprising patients with PFS  $\geq 9$  months.
  - B-Refractory (primary): comprising patients with best response to treatment = PD. This date is collected in the CRF form “axitinib treatment”.
- MSKCC risk group (described in appendix 11.1.). It will be analysed “Before the beginning of the first line”. These calculations will be performed on patients who have data on all the variables involved (in the case of a patient who does not have data on all the variables but has > 2 factors, it will be classified in the “Poor” risk group.

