## 7.1 PRIMARY OBJECTIVE

In order to meet the study's primary objective, the baseline clinical characteristics of two patient groups with extreme response to the drug will be compared: A group of patients with long-term responses to the drug (long-term responders to axitinib) versus a group of patients with disease progression at the first assessment after the initiation of treatment (group of patients refractory to axitinib).

The classification (in long-term responders or refractory patients) will be based on PFS (in months), as indicated in section 5.2.

It will be shown the following descriptive tables:

- “Long responder” patient (Yes, No). “Long responding patient” is defined if he / she has an PFS  $\geq 9$  months (during axitinib treatment). The 95% CI will be displayed.
- PFS in long responding patients. Only the descriptive analysis of the time in months and the CI for the average, will be shown.
- “Refractory” patient (Yes, No). "Refractory patient" is defined if there is a better response to treatment = PE (to axitinib treatment). 95% CI will be shown.
- PFS in refractory patients. Only the descriptive analysis of the time in months and the CI for the average will be shown.
- Patient group (Long respondent, refractory). It is defined in section 5.2. IC95% will be displayed

At the same time, In addition to comparisons of baseline clinical characteristics between the groups (long-term responders, refractory patients), an association analysis of the following factors with the study groups will be performed:

- Age with respect to first visit ( $\leq 65$  years and  $> 65$  years).
- Age with respect to first diagnosis ( $\leq 65$  years and  $> 65$  years).
- Age with respect to start of axitinib ( $\leq 65$  years and  $> 65$  years).
- Baseline ECOG/PS and at the initiation of first line treatment (0, 1 and  $\geq 2$ ).
- Baseline ECOG/PS and at the initiation axitinib treatment (0, 1 and  $\geq 2$ ).
- Baseline ECOG/PS and at the end of axitinib treatment (0, 1 and  $\geq 2$ ).
- Number of previous treatment lines
- Number of previous treatment lines (1, 2 and  $\geq 3$ )
- Previous nephrectomy (yes and no)
- MSKCC (or IMDC) risk group in all moments in which it is analysed during the study (favourable, intermediate and poor)

- Histology (100% clear cells, primarily clear cells, primarily non-clear cells, 100% non-clear cells)
- Duration of first-line treatment

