## 7.2 SECONDARY OBJECTIVES

- Response to treatment with axitinib in the long-term responder group (defined as a PFS of at least 9 months with the drug). The "Best treatment response" variable from the "Treatment with axitinib" form will be analysed in this group of patients.
- Efficacy of axitinib by treatment line (second line treatment and further lines). Note: in treatments following axitinib, the "Date of progression" is not available, so times to progression will not be done.
  - o Treatment line in which axitinib is received (2,  $\geq 3$ ).

The following descriptive analyzes will be performed based on the treatment line on which axitinib has been received (2 vs.  $\geq 3$ ):

- o Best treatment response (CR, PR, SD, DP).
- o Duration of treatment.
- o Progression-free survival (this will not be performed for subsequent treatments).
- o Objective response rate (ORR) and clinical benefit (sum of CR, PR and SD).
- o Time to Progression (this will not be performed for subsequent treatments).
- o Overall Survival.
- Efficacy of axitinib per treatment line depending on the group (LR and Refractories)

A table will be displayed with the number of treatment line in which axitinib has been received in both groups of patients (2,  $\geq 3$ ). Depending on these groups (2,  $\geq 3$ ) the following analyzes will be performed in each of the groups (LR and PR):

- o Best treatment response (CR, PR, SD, DP).
- o Duration of treatment.
- o Progression-free survival
- o Objective response rate (ORR) and clinical benefit
- o Time to Progression
- o Overall Survival.

---

Likewise, a table will be shown with the number of patients with axitinib in the second line of treatment, and in  $\geq 3$  line in each group (long responders and refractories).

The following analyzes will be carried out by group (long responders / refractories):

- Best treatment response (CR, PR, SD, DP).
- Duration of treatment.
- Progression-free survival. PFS will be shown in all patients with axitinib in the second line of treatment, and PFS per group
- Objective response rate (ORR) and clinical benefit.
- Time to Progression
- Overall Survival. OS will be shown in all patients with axitinib in the second line of treatment, and OS per group
- Progression-free survival to sunitinib. PFS will be shown in all patients with axitinib in the second line of treatment, and PFS per group

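### The pooled axitinib efficacy outputs describe a cohort selected on its own outcome, do not estimate efficacy in treated patients, and carry no label saying so

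*SAP*

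**What the plan says.** Protocol 8.2.1 admits patients treated in second line or later "with a PFS equal to or greater than 9 months, or with disease progression in the first response assessment". SAP 2.1 (Analysis population) turns this into two checks. Either "the time from the start of treatment with axitinib to disease progression or death by any cause is" at least 9 months, or best response to axitinib is recorded as PD. The refractory group is defined in the same way in SAP 5.2 ("It means, patients with best response to axitinib=PD") and SAP 7 ("comprising patients with best response to treatment = PD"). The 3-month figure beside it is an estimate; no time limit is imposed.

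SAP 2.1 then states: "All analyses will be performed with evaluable patients". SAP 5.1 agrees: "The full analysis set [FAS] includes all evaluable patients".

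On this cohort the SAP plans the following outputs without splitting by response group:

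- SAP 7.2, by line 2 vs ≥3: "The following descriptive analyzes will be performed based on the treatment line on which axitinib has been received". The endpoints are best response, duration, PFS, ORR and clinical benefit, TTP and OS.
- SAP 7.2, PFS and OS in all patients with second-line axitinib, with the sunitinib-axitinib sequence, and in the subpopulation of special interest.
- SAP 7.2, OS by further treatment, by line, and for the two commonest subsequent treatments.
- SAP 9.2, a reference to PFS, TTP and OS analyses for the total N.

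SAP 7.1 also puts 95% CIs on the group shares: "Patient group (Long respondent, refractory). It is defined in section 5.2. IC95% will be displayed". Separately, SAP 7.2 plans the same by-line endpoints within each response group. Protocol 8.9 names one limitation, the difficulty of predicting how many patients can be included.

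**The concern.** Choosing patients from the two ends of the PFS distribution suits the primary comparison of extremes. It does not suit a pooled summary of PFS, response or clinical benefit, because the selection has already fixed much of the answer.

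Protocol 7.2 asks for a description of efficacy per treatment line. Protocol 6.2 motivates the study by the need for data from normal practice. A reader will therefore tend to take a pooled PFS or ORR from this study as real-world axitinib efficacy, and a difference between lines as a difference in efficacy. Neither reading is available from these patients, and nothing in either document warns against it.

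**Working it through.** The plan derives no figure on this point, so there is none to reproduce. Its expectations are about 60 patients (Protocol 8.5) and about 2:1 long responders to refractory patients (Protocol 3, study population). That is about 40 and 20.

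**Step 1. What follows from the definitions alone.** Let w be the long-responder share.

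- Refractory patients have best response PD, so they contribute no CR, PR or SD. Pooled clinical benefit ≈ w, and pooled ORR = w × (ORR in long responders). If that ORR were 40% (assumed), the pooled ORR at 2:1 would be 0.667 × 40% = 27%.
- No long responder has a PFS event or is censored before 9 months. If all refractory progressions are dated before 9 months, pooled Kaplan-Meier PFS at 9 months equals w.
- At 2:1, w = 40/60 = 0.667 > 0.5, so the pooled median is at least 9 months whatever the PFS of treated patients.
- The exact 95% CI for 40/60 is 53.3% to 78.3%. It describes the mix among eligible enrolled patients.

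**Step 2. Illustration of size and direction.** Assumptions: exponential PFS, and two hypothetical populations with true medians of 4.8 and 6.7 months. Both medians come from Protocol 6.1.6. The first is the prior-sunitinib subgroup and the second the whole axitinib arm of the pivotal trial. They are not line 2 and line ≥3 figures.

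With λ = ln 2 / median and refractory cut-off c:

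- P(PFS ≥ 9) = exp(−9λ): 0.273 and 0.394.
- P(refractory) = 1 − exp(−cλ): at c = 3, 0.352 and 0.267.
- Full capture of eligible patients: w = P(PFS ≥ 9) / [P(PFS ≥ 9) + P(refractory)].
- If w > 0.5, pooled median = 9 + ln(w/0.5)/λ.
- If w < 0.5, pooled median is the t solving 1 − exp(−λt) = P(refractory) × 0.5/(1 − w).

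| Setting | w (true 4.8) | Pooled median | w (true 6.7) | Pooled median | Difference |
|---|---|---|---|---|---|
| True, all treated | – | 4.8 | – | 6.7 | 1.9 |
| 2:1 in both | 0.667 | 11.0 | 0.667 | 11.8 | 0.8 |
| Full capture, c = 2 | 0.521 | 9.3 | 0.678 | 12.0 | 2.7 |
| Full capture, c = 3 | 0.437 | 2.6 | 0.596 | 10.7 | 8.1 |
| Full capture, c = 4 | 0.383 | 3.0 | 0.538 | 9.7 | 6.7 |
| Full capture, c = 5 | 0.346 | 3.5 | 0.494 | 4.9 | 1.4–1.5 |

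Worked cell (6.7 months, c = 3): w = 0.394/(0.394 + 0.267) = 0.596; λ = 0.1035; median = 9 + ln(0.596/0.5)/0.1035 = 10.7.

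The difference of 1.9 months is shrunk in two settings and enlarged in three. The jump at 3 and 4 months arises because the two shares fall on either side of 50%.

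**Step 3. The odds ratio for group membership.** At full capture the long-responder vs refractory odds ratio between these two populations is 1.94, 1.90, 1.87 and 1.84 for c = 2, 3, 4 and 5. For PFS ≥9 vs <9 months in all treated patients it is (0.394/0.606)/(0.273/0.727) = 1.74. It is far more stable than the pooled median, provided inclusion within each group does not depend on line. If line did drive inclusion, with assumed long-responder shares of 75% and 55% and no true effect, it would be (0.75/0.25)/(0.55/0.45) = 2.45.

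**The case against.** The study is declared exploratory and its secondary outputs descriptive. The extreme-group design is stated repeatedly, no passage claims to estimate efficacy in all treated patients, and every pooled PFS has a per-group counterpart. All of this is true, and it keeps the matter to labelling and interpretation. But a descriptive figure still needs its population stated, and a table presented as efficacy of axitinib by line answers a protocol objective in those terms.

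The per-group tables help only in part. Refractory ORR and clinical benefit are zero by definition, and long-responder PFS is at least 9 months by definition.

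Four stronger readings are tempting, and the documents do not support them.

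- A reader might infer that the selection always exaggerates a difference between lines. The table shows enlargement at some cut-offs and shrinkage elsewhere, and the SAP fixes no cut-off.
- A reader might infer that sites included patients differently by line, so that a difference is manufactured. No passage says so, and sites may include every eligible patient.
- A reader might infer that the CIs on the group shares must go. SAP 7.1 does not call the shares response rates, and a CI for the mix among eligible patients has a meaning. A label is enough.
- A reader might infer that the primary comparison fails. It remains usable as a contrast of extremes, if inclusion within each group does not depend on the factor studied.

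**Conclusion.** The concern holds as a point about what the pooled outputs estimate. Pooled clinical benefit and ORR follow from the group definitions and the enrolled mix. So does pooled 9-month PFS, on the condition that refractory progressions are dated before 9 months. None of this needs a PFS distribution. At the expected 2:1 ratio the pooled median is at least 9 months by construction.

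The individual medians in the table rest on exponential PFS, hypothetical populations and assumed cut-offs. They show that the distortion can run either way; they do not predict its size here. Pooled PFS beyond 9 months and OS mix real within-group information with the enrolment mix, and the OS distortion cannot be sized from the documents. This should be fixed before the results are reported.

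**What to change.** 1. Head every pooled efficacy output in SAP 7.2 and 9.2 along the lines of *outcome-selected cohort; not an estimate of axitinib efficacy in treated patients*, and draw no efficacy-by-line conclusion from it.
2. Report the planned per-group by-line tables as conditional on outcome. State which entries are fixed by definition, so that only long-responder depth of response, long-responder PFS beyond 9 months, duration and OS are informative.
3. Label the group shares and their CIs in SAP 7.1 as the mix among eligible enrolled patients, not a response rate.
4. Add to the limitations (Protocol 8.9 and the report) that patients were selected on outcome. Name those who were not eligible: patients who progressed between the first assessment and 9 months, those who died before 9 months without best response PD, and those progression-free with under 9 months of follow-up.
5. Report the line 2 vs ≥3 odds ratio (long responder vs refractory) with its CI, whatever the P<0.15 and P<0.05 screens in SAP 7.1 give, since those screens could drop line. Note that it contrasts extremes, is imprecise with about 20 refractory patients, and is valid only if inclusion within each group does not depend on line.

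SAP 1 gives review after draft results as the reason for its latest amendment, so record these changes as made after draft results. The cost is wording, table headings and one extra estimate, with no new data and no protocol-listed output deleted. The downside is that the study will have no headline real-world PFS or ORR.

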    - Has treatment with axitinib been discontinued? (Yes/No)
      - If yes, specify:
        - End-of-treatment date
        - Reason for suspension of treatment (DP/Toxicity/Other, specify)
    - Risk criteria at discontinuation of treatment with axitinib

- 
- Time from first diagnosis to systemic treatment less than 1 year (Yes/No/Unknown)
    - ECOG/PS (current status) (Yes/No/Unknown)
    - LDH >1.5 x ULN (Yes/No/Unknown)
    - Haemoglobin < LLN (Yes/No/Unknown)
    - Corrected calcium >10 mg/dl (Yes/No/Unknown)
    - Presence of 2 or more metastatic sites (Yes/No/Unknown)
    - Platelets > ULN (Yes/No/Unknown)
    - Neutrophils > ULN (Yes/No/Unknown) (value)
  - Has there been disease progression? (No/Yes, specify date)
  - Best treatment response (CR, PR, SD, DP/Not evaluable).
    - Date of the best response obtained
  - Starting dose (5 mg/12 h; 2 mg/12 h; 3 mg/12 h; 7 mg/12 h; 10 mg/12 h)
  - Has the dose been modified? (Yes/No)
    - If yes, specify:
      - Increased/Reduced
      - Dose modification date
      - Reason for dose modification
      - New dose (5 mg/12 h; 2 mg/12 h; 3 mg/12 h; 7 mg/12 h; 10 mg/12 h; other, specify mg/h)
  - Adverse events
    - Adverse events (Anaemia; Asthenia; Fatigue; Diarrhoea; Dysphonia; Elevated ALT/GPT; Elevated AST/GOT; Elevated Bilirubin; Elevated Creatinine; Elevated Haemoglobin; Elevated Lipase; Hypercalcaemia; Hypertension; Hypocalcaemia; Hypophosphatemia; Hypothyroidism; Lymphopenia; Mucositis; Nausea; Neutropenia; Proteinuria; Rash; Hand-foot syndrome; Thrombocytopenia; Vomiting, Other, specify).
    - Worst grade according to CTCAE
    - Cycle in which the worst grade occurred
    - Related to treatment (Yes/No)
    - Serious AE? (Yes/No), if yes, specify
      - Reason (Results in death/ Is life threatening/ Leads to hospitalisation or prolongation of hospitalisation/ Causes persistent or significant disability or incapacity/ Causes a congenital anomaly or birth defect/ Is medically significant).
  - Subsequent treatments
    - Has the patient received any subsequent treatment? (Yes/No)
      - If yes, specify
        - Drug received
        - Starting dose
        - Treatment line
        - Start date

- End date
- Ongoing
- Best response attained (CR, PR, SD, DP/Not evaluable)
- Reason for discontinuation (DP/Toxicity/Other, specify)
- Vital status
  - Date of last follow-up
  - Status (Alive/Death)
    - If Death, specify
      - Date of death
      - Cause of death (DP, Other, specify)

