It will be calculated as follows: Progression Free Survival to sunitinib (SLP, in months) = (Date of Progression of the Disease to treatment with sunitinib - Start date of treatment with sunitinib) / 30,4375. If there is no progression, the case is censored in SLP (months) = (Start date of treatment with axitinib - Start date of treatment with sunitinib) / 30,4375.

- **Majority sequence**

The number of patients receiving the second-line treatment will be shown, following the sequence that is most observed in all the patients included (SUT-AXI-NIVO).

The following analyzes will be carried out by group (long responders / refractories):

- Best treatment response (CR, PR, SD, DP).
- Duration of treatment (months).
- Progression-free survival. PFS will be shown in all patients with sunitinib-axitinib sequence and PFS per group.
- Objective response rate (ORR) and clinical benefit.
- Time to Progression
- Overall Survival. OS will be shown in all patients with sunitinib-axitinib sequence and OS per group
- Overall Survival since the beginning of 1st line. OS will be shown in all patients with sunitinib-axitinib sequence and OS per group

It is defined as: Global Survival from the beginning of the first line (SG, in months) = (Exit date - Start date of first line treatment) / 30,4375. If there is no exitus the case is censored in Global Survival (SG, in months) = (Date of last control - Start date of the first treatment) / 30,4375.

- To describe the duration of treatment with axitinib. It will be described as it is described in section 7. Definition of variables and objectives
- To describe the percentage of patients who had increase the dose of axitinib above 5 mg twice daily. It will be described as it is described in section 7. Definition of variables and objectives
- To describe the percentage of patients who had reduce the dose of axitinib below 5 mg twice daily. It will be described as it is described in section 7. Definition of variables and objectives
- To describe the tolerability of axitinib (see point 9.2. Statistical analyses, Safety objectives).
- To describe the response to treatments received at progression. The treatments received will be described in cases of DP for first-line, 2nd line, etc.; that is, in treatments prior to axitinib.
- Overall survival based on post treatment
  - o Overall survival. The OS will be displayed according to having received further treatment (Yes vs. No).

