  - o The following analyzes will be carried out in the patient population depending on whether or not they have had subsequent treatment;
    - OS per group (LR vs RF).
    - OS per axitinib line (2 VS  $\geq 3$ ).
    - OS per group (LR vs RF) for patients with axitinib in line 2.
    - OS per group (LR vs RF) for patients with axitinib online  $\geq 3$ .
- Overall survival based on most recent subsequent treatment.

The following analyzes will be performed in this subpopulation of patients in the groups of patients who have had the 2 most common subsequent treatments:

- o OS
- o OS per group (LR vs RF)
- o OS per axitinib line
- o OS per group (LR vs RF) for patients with axitinib online 2
- o OS per group (LR vs RF) for patients with axitinib online  $\geq 3$
- To describe treatments received at progression. The treatments received in the cases of PD for first line, 2nd line etc ... it means, in the treatments previous to axitinib will be described. The analysis of post-axitinib treatments will be shown as explained in section 9.2 Statistical analysis.

The responses of the previous treatments to axitinib initiated by PD in the different registered lines will be presented.

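### Overall survival from axitinib start is split by whether later treatment was ever given, a status fixed after time zero; the direction of the bias depends on an analysis set that SAP 7.2 does not state

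*SAP*

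**What the plan says.** SAP section 7 defines OS as ("Date of death – Date of start of treatment with axitinib) / 30.4375". For patients alive it adds: "If death has not occurred, the case is censored as" the time from axitinib start to the latest follow-up.

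SAP 7.2 then plans an OS analysis by later therapy: "The OS will be displayed according to having received further treatment (Yes vs. No". It continues: "The following analyzes will be carried out in the patient population depending on whether or not they have had subsequent treatment", and lists OS by response group, by axitinib line, and by response group within line. A further item gives OS "in the groups of patients who have had the 2 most common subsequent treatments".

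The grouping comes from one CRF field, "Has the patient received any subsequent treatment? (Yes/No", in SAP section 6. The start date of each later treatment is also recorded. Section 7 uses it for treatment durations, which "will be calculated (from the start date to the end date or last check if it continues".

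The observations under SAP 9.2, Other analyses, limit the subsequent-treatments section to patients whose axitinib was stopped. Section 7.2 does not repeat that limit for the OS split and speaks of the patient population. Neither the SAP nor protocol 8.9 (limitations) mentions a landmark, a time-dependent covariate, a different time origin or a caveat.

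**The concern.** The groups are formed by something that happens after the clock has started. To be Yes, a patient must live through axitinib treatment and through the gap to the next drug. Deaths in that interval can only fall in No. This gives Yes a stretch of guaranteed survival that is not due to the later drug.

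A second distortion pulls the other way. If the split covers all evaluable patients, those still on axitinib at inclusion are also No. They are mostly long-term responders with long event-free time, and they improve the No curve for a reason unrelated to later therapy.

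A table of OS by further treatment (Yes or No) invites the reading that the difference is what later therapy achieved. As planned, the medians and curves cannot support that reading, or even a neutral description, until the analysis set is known.

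**Working it through.** The documents give no event count, effect size or power figure for this output, so there is no planned figure to reproduce. The check asks what the planned split shows when later therapy has no effect at all.

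**Inputs from the documents.** About 60 patients (protocol 8.5). About 2:1 long-term responders to refractory patients (protocol abstract), hence about 40 and 20. Log-rank test at two-sided 0.05 (SAP 9.1). OS from axitinib start (SAP 7).

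**Assumptions, not in the documents.** Refractory patients progress at 1.5–3.5 months. Long-term responders progress at 9 months plus an exponential time of median 8 months. Axitinib stops at progression. Survival after stopping is exponential with median 10 months. The gap to the next drug is exponential with mean g = 0.5, 1, 2 or 3 months. 80% would take a next drug if alive. Follow-up runs up to 60 months.

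**Step 1: the mechanism by hand, with the clock at axitinib end and complete follow-up.** The death rate after stopping is λ = ln 2 / 10 = 0.0693 per month, so mean survival is 1/λ = 14.43 months. Among patients intended for a next drug:

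- The share dying before it starts is λ / (λ + 1/g). For g = 1: 0.0693 / 1.0693 = 0.065. These patients become No, with mean survival 1 / 1.0693 = 0.94 months.
- The Yes mean is 0.94 + 14.43 = 15.36 months (before rounding of its parts).
- The No share is 0.2 + 0.8 × 0.065 = 0.252. The No mean is (0.2 × 14.43 + 0.8 × 0.065 × 0.94) / 0.252 = 11.65 months.
- The ratio of death rates, Yes to No, is 11.65 / 15.36 = 0.76, although every patient has the same hazard.

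The same arithmetic gives 0.86, 0.64 and 0.57 for g = 0.5, 2 and 3. With censoring added by simulation, the ever/never rate ratio on this clock is 0.81, 0.70, 0.57 and 0.51 for g = 0.5, 1, 2 and 3.

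**Step 2: the planned analysis, with the clock at axitinib start and no true effect.** Hazard ratios (HR) are from 120,000 simulated patients. Rejection rates are from 3,000 trials of 60.

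| Mean gap (months) | HR, stopped axitinib only | Log-rank rejects | HR, all patients, ongoing counted as No | Log-rank rejects |
|---|---|---|---|---|
| 0.5 | 0.87 | 8.7% | 1.45 | 15.9% |
| 1 | 0.81 | 10.9% | 1.31 | 10.6% |
| 2 | 0.72 | 18.9% | 1.12 | 6.3% |
| 3 | 0.67 | 24.8% | 1.00 | 5.9% |

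In the stopped set, rejections nearly always favour Yes. In the all-patients set, about 15% are still on axitinib.

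**Step 3: sensitivity.**

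- Stopped set, 1-month gap: HR 0.91 if 50% would take a next drug; 0.72 if 10% of long-term responders die on axitinib; 0.58 if fitter patients are chosen for later therapy; 0.42 if every survivor is treated.
- All-patients set, 1-month gap: HR 4.36 if 44% are still on axitinib (longer progression-free times and shorter follow-up); 0.85 if follow-up is complete and nobody is ongoing.

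**Step 4: remedies under the same null.**

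- Clock at axitinib end, later treatment time-dependent: the rate ratio is 1.00 for all four gaps. With 60 patients the Cox HR is 0.94–1.01, with 4–8% rejections.
- A time-dependent covariate left on the axitinib-start clock: the null HR is about 3.6–7.8. Time on axitinib before progression is low-risk time and all of it counts as untreated. This model had no deaths on axitinib, which makes the contrast as sharp as it can be.

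**The case against.** The strongest defence is that nothing is being claimed. SAP 9.2 makes all secondary objectives descriptive, 7.2 only displays the curves, the log-rank test applies only where a comparison is needed, and no objective concerns the effect of post-axitinib therapy. This stands as a limit on the consequence. It does not repair the output, because the medians and curves are distorted with or without a p-value.

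A second defence is that 9.2 already confines the subsequent-treatment section to patients who stopped axitinib. That may be the intention, but the text does not extend it to the OS items in 7.2. If it did apply, it would remove the ongoing patients from No and leave the guaranteed survival time in place.

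A reader might infer several stronger points that the documents do not support:

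- **That later therapy will look beneficial.** This follows only if No holds few or no ongoing patients. Otherwise the bias can cancel or reverse.
- **That a badly inflated Yes-versus-No test is planned within the roughly 20 refractory patients.** The list in 7.2 reads more naturally as long-term responders versus refractory patients inside each Yes/No stratum, so error rates for that contrast should not be the headline.
- **That the two-most-common-drugs item has the same Yes/No flaw.** Everyone in it received a later drug. Bias between the drugs arises only if the time to starting them differs, and no drug-versus-drug comparison is stated.
- **That the majority-sequence OS is conditional on later nivolumab.** The SAP introduces that set as "following the sequence that is most observed in all the patients included (SUT-AXI-NIVO", but the OS lines refer to the sunitinib–axitinib sequence. The two descriptions need reconciling; the text does not show that nivolumab is required.

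**Conclusion.** The point holds in a limited form. OS from axitinib start, split by ever having later treatment, is biased by construction, and nothing in the plan guards against it. Under the assumptions above, the null HR is about 0.87 to 0.67 among patients who stopped axitinib, and further from 1 if fitter patients are selected. It is about 1.45 to 1.00 if some 15% are ongoing and counted as No, and higher if more are ongoing. A value near 1 in the second case reflects two opposing biases, not a valid comparison.

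The sign therefore cannot be stated until the analysis set is. The size rests on the gap to the next drug, the share treated, deaths on axitinib and selection, none of which the documents give. With a short gap and no selection, the bias in the stopped set is modest. The output is secondary and descriptive, and the comparison of long-term responders with refractory patients on baseline factors is untouched.

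**What to change.** In SAP 7.2, for the Yes/No display:

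1. State the set: patients who stopped axitinib.
2. Start OS at the axitinib end date.
3. Either enter later therapy as a time-dependent covariate on that clock, or classify patients by treatment started before a fixed landmark (for example 2 months after axitinib end) among those still alive and under follow-up. A time-dependent covariate on the axitinib-start clock is not enough.
4. For OS by specific later drug, start the clock at the start of that drug.
5. Reconcile the two descriptions of the majority sequence so that membership of the OS set does not depend on later nivolumab.
6. At minimum, if the curves stay as planned, label them non-comparative and say why.

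The cost is SAP wording and some re-programming. Axitinib end date, later-treatment start dates and date of death are all CRF fields. There are three drawbacks:

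- Patients who die before the landmark leave that table and should be counted in a footnote.
- SAP section 8 sets a missing day to the 15th, an error of at most 16 days, and a missing day and month to 15 June, an error of up to 199 days (15 June to 31 December), or 199 / 30.4375 = 6.5 months. A few patients may be misclassified around a 2-month landmark.
- Neither method removes the selection of fitter patients for further therapy, so the corrected display still should not be read as a treatment effect.
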